### 3.4.2 Exploratory Efficacy Endpoints

The exploratory efficacy endpoints are defined in Section 2.3.3. Descriptive statistics at each scheduled visit for the values and changes from baseline of the exploratory efficacy endpoints will be summarized. For certain efficacy endpoints, logarithmic transformation may be performed prior to fitting the ANCOVA model. Since these endpoints are for exploratory purposes, all the analysis will be based on the observed values and no adjustments for multiplicity will be made expecpt for liver steatosis as evaluated by FibroScan® expressed in CAP.

### 3.4.2.1 Markers of liver injury and function

Markers of liver injury and function including ALT, AST, ALP, GGT, bilirubin, INR, albumin, MELD score, and CP score will be measured at Screening, Pre-Baseline, Baseline (Day 1), Week 1, Week 4, Week 8, Week 12, Week 16 and Week 20 Safety follow-up.

CP score will be calculated as below, ranging from 5-15:

	1 point	2 point	3 point
Bilirubin (Total)	<2 mg/dL (<34.2 μmol/L)	2-3 mg/dL (34.2-51.3 µmol/L)	>3 mg/dL (>51.3 µmol/L)
Albumin	>3.5 g/dL (>35 g/L)	2.8-3.5 g/dL (28-35 g/L)	<2.8 g/dL (<28 g/L)
INR	<1.7	1.7-2.2	>2.2

Ascites	Absent	Slight	Moderate
Encephalopathy	No Encephalopathy	Grade 1-2	Grade 3-4
Class A = 5-6 points			
Class B = 7-9 points			
Class C = 10-15 points			

ANCOVA model with treatment group as a factor and baseline value as a covariate will be used for analyzing the change from baseline to Weeks 4, 8, 12, 16, and 20, as well as the percent change from baseline to Weeks 4, 8, 12, 16 and 20. LS means, 95% confidence intervals and p-values will be presented.

### 3.4.2.2 Body weight and waist-to-hip ratio

Body weight, waist circumference and hip circumference will be measured at all visits.

ANCOVA model with treatment group as a factor and baseline value as a covariate will be used for analyzing the change from baseline and percent change from baseline to Weeks 4, 8, 12, 16, and 20. LS means, 95% confidence intervals and p-values will be presented.

#### 3.4.2.3 Biomarkers

Lipid metabolism biomarkers and insulin sensitivity & glycemic control biomarkers will be measured at Baseline (Day 1), Week 1, Week 4, Week 8, Week 12, Week 16 and Week 20 Safety follow-up.

ANCOVA model with treatment group as a factor and baseline value as a covariate will be used for analyzing the change from baseline to Week 12, the change from baseline to Week 16, and the change from baseline to Week 20, as well as the percent change from baseline to Week 12, 16 and 20. LS means, 95% confidence intervals and p-values will be presented.

#### 3.4.2.4 DXA scan measurements

DXA scans measurements including bone mineral density of the lumbar spine, femoral neck, total hip and body fat distribution will be performed at Baseline (Day 1) and Week 16.

An analysis will be performed on the change from baseline to Week 16 in DXA Scan measurements using ANCOVA model with treatment group as a factor and baseline value as a covariate. LS means, 95% confidence intervals and p-values will be presented.

### 3.4.2.5 Liver biopsy

- The proportion of subjects at Week 16 whose fibrosis regresses by ≥ 1-stage according to the NASH CRN classification
- The proportion of subjects at Week 16 who had no worsening in NAS with improvement in fibrosis stage
- The proportion of subjects at Week 16 who had at least 2 points improvement in NAS
- The proportion of subjects at Week 16 who had ≥ 1 point improvement in NAS, fibrosis, steatosis lobular inflammation or hepatocellular ballooning
- The proportion of subjects at Week 16 who had NASH resolution (0-1 Point Inflammation, 0 Point Ballooning)
- The proportion of subjects at Week 16 who had fibrosis improvement ≥ 2-stage

Following 16 weeks of treatment, subjects will be given the option to collect an end of treatment biopsy. Counts and percentages of subjects will be presented by treatment group based on the Liver Biosy Evaluable Analysis Set using central reads.

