4.2. Inclusion Criteria

Main Study: Subjects must meet all the following inclusion criteria to be eligible for study participation:

- 1. Males and non-pregnant, non-lactating females between 18 80 years of age inclusive, based on the date of the screening visit.
- 2. BMI > 25 kg/m² (unless the subject has biopsy-proven NASH documented within the last 2 years).
- 3. Must have confirmation of $\geq 10\%$ liver fat content on MRI-PDFF at screening.
- 4. Biopsy-proven NASH. Must have had a liver biopsy within 180 days of randomization with fibrosis stage 1 to 3 and a NAS of \geq 4 with at least a score of 1 in each of the following NAS components:
 - a. Steatosis (scored 0 to 3),
 - b. Ballooning degeneration (scored 0 to 2), and
 - c. Lobular inflammation (scored 0 to 3).
- 5. Must have no evidence of worsening of ALT and AST (within 50%) measurements at the screening (-6 weeks) and pre-baseline (-2 weeks) visits.
- 6. Screening laboratory parameters, as determined by the central laboratory:
 - a. Estimated glomerular filtration rate (eGFR) ≥ 60 mL/min, as calculated by the Cockcroft-Gault equation;
 - b. HbA1c \leq 9.5% (or serum fructosamine \leq 381 µmol if HbA1c measurement is unavailable);
 - c. Hemoglobin ≥ 11 g/dL;
 - d. International normalized ratio (INR) \leq 1.3, unless due to the rapeutic anticoagulation;
 - e. Direct bilirubin ≤ 0.3 mg/dL;
 - f. Total bilirubin \leq 1.3 x upper limit of normal ULN, unless due to an alternate etiology such as Gilbert's syndrome or hemolytic anemia;
 - g. Creatinine kinase < 3 x ULN;
 - h. Platelet count \geq 150,000/µL;
 - i. Serum triglyceride level $\leq 500 \text{ mg/dL}$;
 - j. Alanine aminotransferase (ALT) \leq 5 x ULN;

- k. Aspartate aminotransferase (AST) < 5 x ULN;
- 1. AST >20u/L (only required for subjects without a historical biopsy in the last 2 years confirming fibrosis 1-3 and a NAS \geq 4);
- m. Alkaline phosphatase (ALP) < 2 x ULN;
- 7. Subjects on Vitamin $E \ge 400$ IU/day, thiazolidinediones (including, but not limited to, pioglitazone, rosiglitazone, and lobeglitazone), GLP1, or SGLT2 must be on a stable dose (defined as no changes in prescribed dose, new medications, or discontinuation) for at least 6 months prior to the diagnostic liver biopsy and screening.
- 8. Subjects on antidiabetic, weight loss, or lipid-modifying medication(s) must be on stable dose(s) for at least 3 months prior to the diagnostic liver biopsy through randomization.

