- 9. Willing and able to give written informed consent prior to any study specific procedures being performed.
- 10. Female subjects of childbearing potential (see definition in Appendix C) must have a negative pregnancy test at screening and Baseline/Day 1.
- 11. Male subjects and female subjects of childbearing potential who engage in heterosexual intercourse must agree to use protocol specified method(s) of contraception as described in Appendix C.
- 12. FibroScan[®] measurement > 7.0 kPa.

Cohort C: Subjects must meet all the following inclusion criteria to be eligible for study participation:

- 1. Males and non-pregnant, non-lactating females between 18 80 years of age inclusive, based on the date of the screening visit.
- 2. Compensated cirrhosis (Fibrosis Stage 4) due to NASH documented by a local pathologist within 24 months of Screening with no evidence of competing etiology, and at least one co-existing or historic metabolic comorbidity. If a historical biopsy is not available within 24 months of Screening, the subject may undergo a liver biopsy to be assessed by the local or central reader and confirmed to have compensated cirrhosis (Fibrosis Stage 4).
- 3. FibroScan[®] measurement > 13.1 kPa.
- 4. Enhanced Liver Fibrosis (ELF) score of > 9.8.
- 5. Must have no evidence of worsening of ALT and AST (within 50%) measurements at the screening (-6 weeks) and pre-baseline (-2 weeks) visits.
 - a. A single retest of the pre-baseline labs is permitted only if there is reason to believe the initial value was erroneous due to a sample processing error or due to an extenuating circumstance. An average of the screening and pre-baseline value will be used and compared to the retest value. The retest value must have no evidence of worsening within 50% of the average of the screening and pre-baseline value.
- 6. Screening laboratory parameters, as determined by the central laboratory:

- a. Estimated glomerular filtration rate (eGFR) \ge 60 mL/min, as calculated by the Cockcroft-Gault equation;
- b. HbA1c \leq 9.5% (or serum fructosamine \leq 381 µmol if HbA1c measurement is unavailable);
- c. Hemoglobin ≥ 11 g/dL;
- d. International normalized ratio (INR) \leq 1.3, unless due to the rapeutic anticoagulation;
- e. Direct bilirubin ≤ 0.3 mg/dL;
- f. Total bilirubin \leq 1.3 x upper limit of normal ULN, unless due to an alternate etiology such as Gilbert's syndrome or hemolytic anemia;
- g. Creatinine kinase < 3 x ULN;
- h. Platelet count \geq 125,000/µL;

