6.7. Liver Biopsy

Main Study:

A liver biopsy must be obtained at screening and between weeks 22-24 (for subjects with \geq 30% relative fat reduction on MRI-PDFF at Week 12) to provide the liver tissue for central reading. All reasonable attempts should be made to acquire a liver biopsy specimen of at least 2.0 cm in length. It is recommended that a 16-gauge needle is used to collect the tissue sample.

A historical biopsy that meets eligibility criteria may be accepted as the screening biopsy if the sample is deemed acceptable for interpretation by the central reader. The historical sample must have been originally obtained within 180 days of the Randomization date and confirm the below criteria:

- Subject was not previously treated for NASH/NAFLD with prohibited concomitant medications (including investigational products) within 6 months of historical biopsy.
- Subject was not previously treated with an Investigational Product within 6 months prior to or at the time of historical biopsy.

If the historical biopsy is not adequate for interpretation by the central reader, or was obtained more than 180 days prior to randomization, a fresh liver biopsy will be collected. Liver biopsies will be sent to a central laboratory and then read by a central reader. The central reader will read all screening biopsies for eligibility.

Cohort C:

A historical biopsy performed within 24 months of the Screening Visit or for those subjects who undergo a liver biopsy for eligibility, the following is required for enrollment:

- Biopsy must be consistent with NASH and cirrhosis as assessed by a local pathologist.
- Subject was not previously treated for NASH/NAFLD (including investigational products unless documentation can be provided that the subject was randomized to placebo) between obtaining the historical biopsy and the Screening visit.

Following 16 weeks of treatment, subjects will be given the option to collect an end of treatment biopsy. Both the historical biopsy sample used to qualify the subject at screening as well as the end of treatment biopsy sample will be shipped for blinded pathology analysis by the central reader.

All Subjects:

If a liver biopsy is performed per standard of care outside of protocol mandated assessments, all possible attempts should be made to submit the biopsy specimen to the central reader for evaluation.

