### 3.2.8 Liver Biopsy Evaluable Analysis Set

Liver Biopsy Evaluable Analysis Set will be a subset of the FAS. It will include all FAS subjects with confirmed F4 fibrosis at baseline by central reads who have Baseline and Week 16 liver biopsy results. It will be the analysis population for the responders based on histologic evaluation of NAS system and fibrosis stage.

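### Cohort C's exploratory NASH resolution row is scored on the Week 16 biopsy alone, so a subject who already meets the definition at baseline and does not change would count as resolved

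*SAP*

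**What the plan says.** The endpoint is "The proportion of subjects at Week 16 who had NASH resolution (0-1 Point Inflammation, 0 Point Ballooning" (SAP 3.4.2.5; also listed in 2.3.2, and in Section 6 as an addition to the protocol). It has no baseline condition and no change term. The biopsy rows are presented as counts and percentages by arm, "based on the Liver Biosy Evaluable Analysis Set using central reads".

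That set comprises "all FAS subjects with confirmed F4 fibrosis at baseline by central reads who have Baseline and Week 16 liver biopsy results" (SAP 3.2.8). It has a condition on baseline fibrosis stage but none on NAS, ballooning or inflammation.

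Cohort C entry (Protocol 4.2, criterion 2) asks for "Compensated cirrhosis (Fibrosis Stage 4) due to NASH documented by a local pathologist within 24 months of Screening". If no such biopsy exists, a new one may be read locally or centrally. Protocol 6.7 adds for Cohort C: "Biopsy must be consistent with NASH and cirrhosis as assessed by a local pathologist". Neither section sets a minimum NAS or component score for this cohort.

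The Main Study does set one. Protocol 4.2, criterion 4, requires NAS of at least 4 with at least 1 point each for steatosis, ballooning and lobular inflammation, and Protocol 6.7 has the central reader read every Main Study screening biopsy for eligibility.

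**The concern.** A resolution rate is normally read as the share of subjects who had active steatohepatitis and lost it. That reading needs everyone in the denominator to have had the condition at the start, on the same reader's scoring. In the Main Study the entry criteria secure this: with ballooning of at least 1, nobody can meet the definition at baseline. The Cohort C SAP adds the endpoint without that protection.

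Five of the six rows in SAP 3.4.2.5 are framed as improvement or regression, so an unchanged liver cannot score on them. The resolution row is the only one defined purely as a state, and so the only one that an unchanged liver can satisfy.

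What is at stake is the meaning of a descriptive percentage. The cohort is small and the end-of-treatment biopsy is optional, so a single subject moves the figure visibly.

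**Working it through.** There is no stated figure to reproduce: the SAP gives no expected rate for this row, and SAP 2.2.2 says the Cohort C efficacy comparisons are not powered. The check is logical first, with arithmetic only as illustration.

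**Step 1. Can a subject in the denominator meet the definition at baseline?**

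| Condition | Main Study | Cohort C |
|---|---|---|
| Minimum NAS | 4 (Protocol 4.2) | none |
| Minimum ballooning | 1 | none |
| Minimum lobular inflammation | 1 | none |
| Reader who qualifies the biopsy | central (Protocol 6.7) | local; local or central if newly taken (Protocol 4.2) |
| Reader for the endpoint | not at issue here | central (SAP 3.4.2.5) |
| Extra condition from the analysis set | not at issue here | central F4 and paired biopsies (SAP 3.2.8) |

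In the Cohort C column, nothing excludes a subject centrally read as ballooning 0 and inflammation 0 or 1 at baseline. The nearest safeguard is the local judgement that the biopsy is consistent with NASH. It makes such a subject less likely, but it carries no score threshold and need not come from the reader who scores the endpoint. The SAP itself allows for local and central reads to differ: 3.2.3 defines a safety set without subjects whose F4 stage is not centrally confirmed, and 3.3.4 tabulates both reads.

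**Step 2. What does one such subject do to the rate?**

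Inputs: Cohort C plans 20 EFX and 10 placebo subjects (Protocol 5.2.2). The number of paired biopsies is not given; 10 EFX and 5 placebo is an assumption.

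Contribution of one already-resolved, unchanged subject = 1/n.

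- All planned subjects biopsied: 1/20 = 5 points (EFX), 1/10 = 10 points (placebo).
- Assumed 10 and 5 biopsied: 1/10 = 10 points (EFX), 1/5 = 20 points (placebo).

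**Step 3. The general form.**

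Let b be the share of evaluable subjects meeting the definition at baseline and remaining there, and r the resolution rate among the rest.

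- Rate as planned = b + (1 - b) × r.
- Rate among those not already resolved = r.

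The documents do not give b. Over an assumed range of 0 to 30%:

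| b (assumed) | planned rate if r = 0 | planned rate if r = 20% |
|---|---|---|
| 0% | 0% | 20% |
| 10% | 10% | 0.10 + 0.90 × 0.20 = 28% |
| 20% | 20% | 0.20 + 0.80 × 0.20 = 36% |
| 30% | 30% | 0.30 + 0.70 × 0.20 = 44% |

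At b = 0 the two definitions agree and nothing is lost by restricting.

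**Step 4. A whole-subject example (assumed counts).** Of 10 EFX subjects, one meets the definition at baseline and stays there, and 2 of the other 9 resolve: 3/10 = 30% as planned, 2/9 = 22% restricted. Of 5 placebo subjects, one is already there and none of the other 4 resolves: 1/5 = 20% as planned, 0/4 = 0% restricted.

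**The case against.** The strongest reply concerns impact. The row is exploratory, was added in the SAP, comes from optional biopsies in a cohort whose primary objective is safety, and is reported without a test, interval or p-value. That stands, and it limits the weight of the point.

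Second, SAP 3.3.4 already tabulates central-read baseline NAS components by arm, for each analysis population that differs in composition from all randomized subjects, and SAP 3.1.4 provides for listing individual data. At this size a reader could find any subject concerned. This is a real mitigation, but the table shows each component separately. Whether one subject has both ballooning 0 and inflammation 0-1 has to be worked out from the listings, and the reported percentage would still count that subject as resolved.

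Three stronger readings are tempting, and the documents do not support them.

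- A reader might infer that the rate must have a floor above zero. It has one only if at least one evaluable subject met the definition at baseline and stayed there. Nothing shows that any did, and a baseline ballooning score of 0 can be read as 1 at Week 16; Protocol 1.5 itself names sampling error and variable interpretation as limits of biopsy.
- A reader might infer that a treatment comparison is compromised. The SAP plans no formal comparison for this row.
- A reader might infer that the row for an improvement of at least 2 NAS points needs the same repair, because a subject with baseline NAS 0 or 1 cannot achieve it. Keeping such subjects in that denominator is a conservative convention and cannot produce a false responder.

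**Conclusion.** The point holds as a gap in the definition: under the text as written, an unchanged subject can be counted as resolved, and neither entry nor the analysis set prevents it. The resolution percentage in Cohort C may therefore include baseline status.

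Its size cannot be determined from the documents. The effect is nil if every evaluable subject has central baseline ballooning of at least 1 or inflammation of at least 2. If one does not, and stays unchanged, the distortion in that arm is 5 points (EFX) or 10 points (placebo) with every planned subject biopsied, and 10 or 20 points with the assumed 10 and 5 biopsies. The shares used in the table above are assumptions, not estimates.

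The consequence is confined to one exploratory, descriptive row. The cohort's safety objective, its secondary endpoints and the other five biopsy rows are unaffected.

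**What to change.** In SAP 3.4.2.5, define the denominator of the NASH resolution row as members of the Liver Biopsy Evaluable Analysis Set who do not already meet the definition on the central baseline read, that is, with baseline ballooning of at least 1 or lobular inflammation of at least 2. Report the number excluded in each arm beside the percentage. Keep the full-set result as a listing, so that subjects resolved at baseline remain visible, including any who worsen. Make the matching edit in SAP 2.3.2 and Section 6. Leave the denominator of the row for at least 2 points of NAS improvement as it is.

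The cost is a few lines of SAP text and one derived flag. The central baseline components are already tabulated under SAP 3.3.4, so no new data or visits are needed. The downside is a smaller denominator for this row, in a table that is already small, and one that differs from its neighbours; a footnote should say so. The change belongs before the Cohort C database is unblinded. After that, SAP Section 1 requires it to be documented as a deviation in the study report.

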#### 3.4.2.6 HRQoL

HRQoL including Short Form 36 Health Survey (SF-36), Chronic Liver Disease Questionnaire-Nonalcoholic Fatty Liver Disease (CLDQ-NAFLD) and Work Productivity and Activity Impairment (WPAI) will be collected at Baseline (Day 1), Week 1, Week 4, Week 8, Week 12, and Week 16.

ANCOVA model with treatment group as a factor and baseline value as a covariate will be used for analyzing the change from baseline to Week 12 and the change from baseline to Week 16. LS means, 95% confidence intervals and p-values will be presented.

SF-36: The SF-36 asks 36 questions to measure functional health and well-being from the subject's point of view. It consists of eight health domains in the table below. These health domain scales contribute to the physical health and mental health summary measures.

The scores are weighted sums of the questions in each domain. All the raw scores will be transformed to scores ranging from 0 - 100. Higher scores represent better health. Physical Component Summary (PCS) is calculated by positively weighting the four subscales in the physical domain (PF, RP, BP and GH) and the remaining psychological domain subscales negatively. In contrast, the Mental Component Summary (MCS) is calculated by positively weighting the four mental domain subscales (VT, SF, RE and MH), and negatively weighting the four physical domain subscales.

Domains	Number of Items	Items
Physical functioning (PF)	10	3, 4, 5, 6, 7, 8, 9, 10, 11, 12
Role-physical (RP)	4	13, 14, 15, 16
Bodily pain (BP)	2	21, 22
General health (GH)	5	1, 33, 34, 35, 36
Vitality (VT)	4	23, 27, 29, 31
Social functioning (SF)	2	20, 32
Role-emotional (RE)	3	17, 18, 19
Mental health (MH)	5	24, 25, 26, 28, 30

CLDQ-NAFLD: The CLDQ-NAFLD asks questions related to liver disease and specifically NAFLD, to measure health related quality of life in subjects with chronic liver disease.

The questionnaire has 36 items grouped into six domains: Abdominal Symptoms, Activity, Emotional, Fatigue, Systemic Symptoms, and Worry. Items are scored by a 7-point rating scale from 1 (all of the time) to 7 (none of the time). The higher item values indicate better health. The domain score will be calculated as dividing the sum of the domain's items by the number of items within that domain. The total score will be calculated as an average of the six domain scores.

Domains	Number of Items	Items
Abdominal Symptoms (AS)	3	1, 5, 17
Fatigue (FA)	6	2, 4, 8, 11, 13, 35
Systemic Symptoms (SS)	6	3, 6, 21, 23, 27, 36
Activity (AC)	5	7, 9, 14, 30, 31
Emotional Function (EF)	9	10, 12, 15, 16, 19, 20, 24, 26, 34
Worry (WO)	7	18, 22, 25, 28, 29, 32, 33

WPAI: The questionnaire asks questions regarding the effect of NASH on a person's ability to work and perform regular activities.

The WPAI consists of six questions: 1 = currently employed; 2 = hours missed due to specified problem; 3 = hours missed other reasons; 4 = hours actually worked; 5 = degree problem affected productivity while working; 6 = degree problem affected regular activities. WPAI

outcomes are expressed as impairment percentages, with higher numbers indicating greater impairment and less productivity. Four main outcomes can be generated and expressed in percentages by multiplying the following scores by 100:

- Percent work time missed due to problem: Q2 / (Q2 + Q4)
- Percent impairment while working due to problem: Q5 / 10
- Percent overall work impairment due to problem:
   Q2 / (Q2 + Q4) + [(1 (Q2 / (Q2 + Q4))) x (Q5 / 10)]
   For those who missed work and did not actually work in the past seven days, the percent overall work impairment due to problem will be equal to the percent work time missed due to problem.
- Percent activity impairment due to problem: Q6 / 10

